9.2. Outcome Measures for Evaluation of Efficacy

Linear mixed effects modeling will be used to examine the association between treatment group assignment (AAT + BWL or wait-list control group coded as a (0,1)-indicator) and binge eating, eating self-efficacy, depressive symptoms, weight, blood pressure, and waist circumference scores at 2 and 6 months. Baseline scores will be used as covariates in these analyses with interactions between treatment group assignments with baseline values of outcome scores. Standardized mean differences (e.g., Cohen's d with bias adjustment) will also be calculated as an effect size measure with 95% CI. Standardized residuals will be examined to assure no assumptions are violated.

9.3. Outcome Measures for Evaluation of Safety

[e.g., rate of hospitalization, rate of safety events, rate of drop-outs due to adverse events]

N/A

9.4. Other Outcomes in the Causal Pathway

N/A

9.5. Baseline Characteristics of the Participants

Non-Latino Black women, over 18 years of age, have a BMI $\geq 25\text{kg/m}^2$, and report at least one binge eating episode weekly.

9.6. Variables Representing Treatment

N/A

10. Statistical Analysis Plans

10.1. Strategies that Apply to all the Specific Aims

To help ensure replicability of the research, the analysis plans will be reviewed and finalized prior to collection of data (a priori). For each specific aim, the analysis plans specify detailed steps for obtaining estimates of population parameters (e.g., treatment effects) and for making inferences.

Sensitivity analyses will be performed to assess the robustness of the major results as indicated by their sensitivity to reasonable perturbations of the choices of the methods and assumptions used. Any question about the optimal choice of methods and assumptions are best handled by relegating competing approaches to roles in the domain of sensitivity analyses. Results of the sensitivity analyses will be used to guide our level of trust in the main results. Best practices for dealing with incomplete data will depend on the documented causes of missing, censored, and coarsened values. The reasons for missing data values, drop-out, and protocol departures will have been documented in/with the database.

All hypothesis tests yielding p-values that are deemed to be not statistically significant will be reported as being inconclusive. The proposed statistical analysis strategy acknowledges that no p-value can reveal the plausibility, presence, truth, or importance of an association or effect--which is consistent with the statements of the American Statistical Association [4,5], the recommendations in Nature [6,7], and guidances, such as the CONSORT Statement [1], STROBE Statement [2], and ICMJE guidance [3].²

10.2. Description of the Study Cohort

Descriptive analyses will first be performed overall, by treatment group, and time points to identify any data anomalies (e.g., missing data, outliers, non-normality) that may invalidate study findings. Remedial measures (e.g., single/multiple imputation of missing data, score/data transformation) will be applied as indicated based on the results of data screening.

² [1] www.consort-statement.org; [2] www.strobe-statement.org; [3] www.icmje.org; [4] Wasserstein RL, et al. (2016), The ASA's Statement on p-Values, *The American Statistician*, 70:2, 129-133. [5] Wasserstein RL, et al. (2019), Moving to a World Beyond $p < 0.05$, *The American Statistician*, 73:sup1, 1-19. [6] Amrhein, et al. (2019) Scientists rise up against statistical significance, *Nature* 567, 305-307. [7] Editorial (2019) It's time to talk about ditching statistical significance: Looking beyond a much used and abused measure would make science harder, but better. *Nature* 567, 283-283.

10.3.Aim-Specific Plans

Plans for Aim 1: [e.g., to evaluate Efficacy, characterize and compare two treatment regimens]

To evaluate the feasibility and acceptability of 6-month AAT + NUTR, we will examine several feasibility outcomes. To assess the feasibility of recruiting adult, AA women to the proposed study, the percent of eligible women who were enrolled and retained in the study will be examined and reasons for nonparticipation and attrition will be documented. Feasibility will also be determined by calculation of point and interval estimates (95% confidence intervals using sample size methods) of the feasibility parameters (proportion/percentages in terms of eligibility, participation, retention; means/medians for attendance at intervention sessions) and bivariate frequency distributions.

Plans for Aim 2: [e.g., to evaluate Safety, characterize and compare two treatment regimens]

At 4 and 6 months, compare changes in (a) binge eating, eating self-efficacy, and depressive symptoms and (b) weight for participants in the AAT vs. control group. Linear mixed effects modeling will be used to examine the association between treatment group assignment (AAT + BWL or wait-list control group coded as a (0,1)-indicator) and binge eating, eating self-efficacy, depressive symptoms, weight, blood pressure, and waist circumference scores at 2 and 6 months. Baseline scores will be used as covariates in these analyses with interactions between treatment group assignments with baseline values of outcome scores. Standardized mean differences (e.g., Cohen's d with bias adjustment) will also be calculated as an effect size measure with 95% CI. Standardized residuals will be examined to assure no assumptions are violated.

Plans for Aim 3: N/A

Plans for Aim 4: N/A

10.4.Planned Interim Analyses (If Applicable)

N/A

10.5.Plans for Coping with Withdrawals and Loss-To-Follow-Up

Enrolled participants who discontinue/are withdrawn will not be replaced. The initial target number of enrolled participants is large enough to cope with loss of participants' data due to discontinuation, withdrawal, or insufficiently complete data (missing values).

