Intervention	
Participants will participate in an 16-week combined Appetite Awareness Training (AAT) + Diabetes Prevention Program (NUTR) intervention. For the first 8 weeks, participants will attend 8 weekly AAT sessions and then transition to eight, weekly NUTR sessions. All sessions will be 60-90 minutes. The goal of AAT is to enable participants to be able to relearn their stomach's hunger signals and begin to obey and monitor functions of satiety. AAT has been successful in helping participants diagnosed with eating disorders reduce binge eating, overeating, and prevent weight gain. Sessions involve didactic training, review of self-monitoring of eating episodes, and homework assignments. NUTR includes group sessions that are based on the Diabetes Prevention Program curriculum, and include content on nutrition (e.g.,

	shopping, fruit and vegetable intake, eating away from home), physical activity, and goal setting.
Study Description	
This study is a two-arm, randomized controlled trial to examine the feasibility and acceptability of 6 month AAT + NUTR compared to wait-list control. Patients will be recruited from the UNC Department of Family Medicine. AAT+NUTR participants will spend the first 2 months receiving treatment to reduce binge eating (AAT), and the next 2 months engaging in group-based nutrition counseling. Participants will then work independently for 2 months. Data from both intervention groups will be collected at 3 time points: baseline, before randomization (T1), at the end of month 4, post treatment (T2), and at the end of month 6, follow-up (T3). Descriptive analyses will first be performed overall, by treatment group, and time points to identify any data anomalies (e.g., missing data, outliers, non-normality) that may invalidate study findings. Remedial measures (e.g., single/multiple imputation of missing data, score/data transformation) will be applied as indicated based on the results of data screening.

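### Section 10.2 lets single imputation and outcome transformation be chosen after by-arm screening with no decision rule; common single imputation of missing outcomes would make Aim 2 standard errors too small

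*Combined protocol and SAP*

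**What the plan says.** Section 10.2 opens with the screening step: "Descriptive analyses will first be performed overall, by treatment group, and time points to identify any data anomalies". Missing values, outliers and non-normality are its examples of anomalies. The rule for acting on them follows: "Remedial measures (e.g., single/multiple imputation of missing data, score/data transformation) will be applied as indicated based on the results of data screening". The Synopsis (Study Description) has the same rule, with remedies that "will be applied as indicated based on the results of data screening".

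Section 10.1 says the plans are closed before data collection and that, for each aim, "the analysis plans specify detailed steps for obtaining estimates of population parameters". On missing data it says: "Best practices for dealing with incomplete data will depend on the documented causes of missing, censored, and coarsened values". Doubts about the best method are "best handled by relegating competing approaches to roles in the domain of sensitivity analyses".

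For Aim 2, Section 10.3 names the model: "Linear mixed effects modeling will be used to examine the association between treatment group assignment" and the outcomes, with baseline scores as covariates. Standardized mean differences with 95% confidence intervals are to be reported as well. It does not say whether the model is fitted to observed or to imputed data.

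Section 10.5 says withdrawals are not replaced and that enrolment is large enough to absorb losses, without giving a rate. No section states which form of single imputation is meant, what would be imputed, what finding would trigger imputation or transformation, or whether the person who screens is blind to arm.

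**The concern.** Two separate problems follow from one sentence.

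The first is precision. Filling each missing outcome once and then analysing the completed data as if every value had been observed counts participants who gave no information. For the usual fill-in methods the standard error comes out too small, so the interval for the treatment difference is too narrow. The mixed model already named for Aim 2 can use the observed follow-up values directly, so there is no need to fill in outcomes before fitting it.

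The second is selection. If the outcome scale is chosen after outcomes have been viewed by arm, the choice can follow the observed difference. This does not shrink the standard error. It means that the reported analysis is one of several that could have been reported.

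At stake is whether the Aim 2 differences and their 95% intervals convey the uncertainty that the trial really leaves.

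**Working it through.** **Inputs.** From the documents: 60 participants, equal arms, d = 0.74, power 0.80 (Section 10.6); 24 per arm as the alternative size (Synopsis, Sections 3.1 and 5.1); pilot retention of 88%, so 12% loss (Section 2.2). Assumed, because the documents give no value: two-sided alpha 0.05 (in line with the 95% intervals), missing completely at random and equally in both arms, baseline correlation 0.5, and loss of 20% or 30% as a range.

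**Step 1, the plan's own figure.** Two-sample t-test with 30 per arm: noncentrality 0.74 × sqrt(30 × 30 / 60) = 2.87 on 58 degrees of freedom. Two-sided power is 0.805, against the stated 0.80. A one-sided test gives 0.882 and does not fit. So 30 per arm with a two-sided 5% level is a fair basis.

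**Step 2, closed form for arm-mean imputation.** Let n be the number randomized per arm and m the number observed. Imputing the arm mean leaves the difference unchanged, so its true standard error is s × sqrt(2/m). The completed data report s × sqrt((m−1)/(n−1)) × sqrt(2/n). The ratio of reported to true is sqrt((m−1)/(n−1)) × sqrt(m/n).

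- n = 30, m = 26: sqrt(25/29) × sqrt(26/30) = 0.864, so 14% too small.
- n = 30, m = 24: sqrt(23/29) × sqrt(24/30) = 0.797, so 20% too small.

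The implied type I error is 2 × (1 − Φ(1.96 × ratio)), which is about 9% and 12%.

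**Step 3, simulation under no effect.** The analysis was ANCOVA at one follow-up, with 5,000 runs per setting and Monte Carlo error of about 0.3 points on type I error. Each cell gives model SE / true SE, then type I error.

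| Per arm: missing | Observed only | Arm mean | Regression | One stochastic draw | Baseline carried forward |
|---|---|---|---|---|---|
| 30: 4 (13%) | 0.977; 5.4% | 0.850; 9.2% | 0.842; 9.7% | 0.861; 9.1% | 0.972; 5.6% |
| 30: 6 (20%) | 0.991; 4.8% | 0.784; 12.4% | 0.786; 12.3% | 0.814; 11.0% | 0.993; 4.5% |
| 30: 9 (30%) | 0.964; 5.9% | 0.672; 18.4% | 0.665; 18.4% | 0.728; 15.3% | 0.966; 5.9% |
| 24: 3 (13%) | 0.999; 5.0% | 0.870; 8.4% | 0.869; 8.5% | 0.888; 8.1% | 1.001; 4.6% |
| 24: 5 (21%) | 0.997; 4.7% | 0.785; 12.0% | 0.780; 12.4% | 0.816; 10.2% | 0.997; 4.8% |
| 24: 7 (29%) | 0.997; 4.7% | 0.696; 16.7% | 0.693; 16.6% | 0.756; 13.1% | 1.002; 4.7% |

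For the three middle methods with 30 per arm, the nominal 95% interval covers 100 − 9.7 to 100 − 9.1, or 90.3-90.9%, at 4 of 30 missing. It covers 87.6-89.0% at 20% missing. Observed-data analysis is an exact 5% test under these assumptions, so its 5.9% at 30% missing is simulation noise.

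**Step 4, choice of scale.** Null data were skewed counts (negative binomial, assumed mean 6 and dispersion 1) with 30 per arm and 6,000 runs. A t-test on the raw scale rejects in 4.8%. Taking the smallest p-value of raw, square-root and log scales rejects in 7.2%. This is a worst case.

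**The case against.** Single imputation is one listed option, and Section 10.2 does not say what would be imputed. It could mean scale items or a missing baseline score, and the mixed model does not by itself handle a missing covariate. Null simulations on the same design, with 13-30% missing, gave SE ratios of 0.97-1.01 and type I error of 4.6-5.7% for mean-imputed baseline covariates, and 0.98-1.01 and 4.7-5.5% for person-mean imputation of items. Baseline carried forward also kept its standard error. This stands: a reader might infer that every form of single imputation gives false precision, and that is not so. The harm belongs to common ways of filling in whole missing outcomes, which the text allows.

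A reader might also infer that Section 10.2 flatly contradicts Section 10.1. A data-dependent step can be prespecified, and Section 10.1 itself ties missing-data handling to documented causes. The real conflict is narrower: detailed steps are claimed, and here no rule is given. Sending competing methods to sensitivity analyses does not fill the gap, because the main method is never named.

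The screen described is for anomalies, not for favourable p-values, so the 7.2% needs conduct that the plan does not state. It shows a possible size only.

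Finally, Aim 2 is secondary, Section 10.6 puts feasibility ahead of efficacy, and Section 10.1 warns against over-reading p-values. That limits the consequence. A reader might suppose that these estimates will size the next trial; Section 10.6 says only that a larger study follows if the pilot succeeds.

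**Conclusion.** The concern holds in a limited form. One option that the plan expressly permits, if used on whole missing follow-up outcomes in its common forms, gives standard errors about 14-16% too small at a loss near the pilot's, and about 19-22% too small at 20% loss. Type I error is then about 9-10% and 11-12%. With 24 per arm it is 8.1-8.5% at 3 of 24 missing and 10.2-12.4% at 5 of 24.

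These sizes rest on equal loss completely at random, a baseline correlation of 0.5, and ANCOVA at one follow-up standing in for the planned mixed model with its group-by-baseline interaction. The 13% case leans on a pilot whose binge-eating result is given at 8 weeks, whereas this trial follows participants for 6 months. The 20% and 30% rates are assumptions. Transformation carries a selection risk and not a standard-error fault.

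The point is worth acting on because a stated option is inferior to a method the plan already names, but it is of moderate weight.

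**What to change.** In the Synopsis and Section 10.2:

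- Remove single imputation of missing follow-up outcomes. Simple imputation of a missing baseline covariate or of isolated scale items may stay, if the rule is written down.
- State that the main Aim 2 analysis is the mixed model of Section 10.3, fitted by likelihood to all observed month 4 and month 6 values, with multiple imputation as a sensitivity analysis under Section 10.1. In the same edit, reconcile the model sentence in Sections 9.2 and 10.3, which refers to months 2 and 6, with the months 4 and 6 given elsewhere.
- Fix each outcome's scale in advance, or choose it on data pooled over arms without arm labels.
- Keep the description of missingness by arm. Pooling the whole screen would hide differential loss.

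The cost is SAP wording only. Intervals will be wider than after single imputation: at 4 of 30 missing the mean model SE is 0.241 on observed data against 0.208-0.223 for the three imputation methods, so 8-16% wider (0.241/0.223 = 1.08; 0.241/0.208 = 1.16). That is the uncertainty single imputation would have hidden.

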The proposed study will use a randomized controlled clinical trial design. A sample of 60 black women who report at least weekly binge eating episodes will be randomized to 2 arms of a 6-month AAT + BWL intervention: AAT+BWL or a control group. AAT+BWL participants will receive an 8-week AAT program, and an 8-week BWL program, both using a group format. Assessments will be conducted at 0, 4, and 6 months. This study will be conducted at one site: UNC Department of Family Medicine.

The goal of AAT is to enable participants to be able to relearn their stomach's hunger signals and begin to obey and monitor functions of satiety 11. AAT has been successful in helping participants diagnosed with Binge Eating Disorder (BED) and bulimia nervosa reduce binge eating, overeating, urges to eat in response to non-appetite stimuli, and prevent weight gain. 12-14 The AAT intervention includes eight 60-minute group sessions. All sessions involve didactic training, review of self-monitoring of eating episodes, interactive activities, and homework assignments to enable participants to practice learned skills. Participants will be provided a workbook, which will include session content, and self-monitoring forms.

The curriculum for BWL (behavioral weight loss) will be based on the evidenced-based curriculum from the Diabetes Prevention Program, or Prevent T2. Eight weekly session will review core content including healthy eating, increasing physical activity, and caloric balance. An outline of session curriculum is attached to the protocol.

[figure not shown]
Physical measures will be taken by trained staff, who will be supervised by [name], PI of this project. The following equipment will be used:

- 1. Height /Weight** will be measured on a digital scale and a wall-mounted stadiometer.
- 2. Waist Circumference** will be measured twice with a Gullick II measuring tape.
- 3. Blood pressure** assessment will be measured using an GE Dinamap Procure Auscultatory 400 Multi-Parameter Patient Monitor with the subject in a sitting position after at least a minute rest period.

Questionnaires:

- 1. Eating Disorder Examination (EDE-Q)** is a self-reported questionnaire based on the Eating Disorder Examination.
- 2. Beck Depression Inventory (BDI)24** is a 21-item questionnaire that measures symptoms and attitudes associated with depression.

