5.1. Treatment Design

The proposed study will use a randomized clinical trial design. A sample of 48 Non-Latino, AA women (BMI ≥ 25 kg/m²; rationale: *prior clinical and research experience suggests that AA women within this BMI range are most likely to identify their eating as problematic and engage in a clinical intervention*²⁶) who report at least weekly binge eating episodes will be randomized to 2 arms of a 6-month intervention: **AAT + NUTR** or **wait-list control**. **AAT + NUTR** participants (n=24) will first receive a weekly, group-based AAT program for the first two months, and then will begin NUTR and receive weekly, group sessions for the next 2 months. **Wait-list control group** (n=24) participants will receive an abbreviated AAT treatment at the end of 6 months. Following the intervention, UNC WMP providers (e.g., social workers, preventive medicine residents), and participants will be asked to participate in a 30-60 minute interview on the acceptability of the AAT +NUTR program, and to explore factors that will increase dissemination and uptake in the primary care setting.

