5.2. Experimental / Observational Design

The proposed study will use a randomized clinical trial design. A sample of 60 black women who report at least weekly binge eating episodes will be randomized to 2 arms of a 6-month AAT + BWL intervention: AAT+BWL or a control group. AAT+BWL participants will receive an 8-week AAT program, and an 8-week BWL program, both using a group format. Assessments will be conducted at 0, 4, and 6 months.

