8.4. Study Visits (Numbered as V1, V2, etc., Day X ± Y)

Participants will attend 8 weekly AAT sessions and then transition to eight, weekly NUTR sessions. All sessions will be 60-90 minutes.

V1: Data on AAT group and control group collected at baseline, before randomization (T1)

V2: Data on AAT group and control group collected at end of month 4, after completion of intervention program (T2)

V3: Data on AAT group and control group collected data end of month 6, posttreatment follow-up (T3)

Data collected includes height, weight, blood pressure, and waist circumference.

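### Up to month 6 only the active arm is treated in groups, but the Aim 2 plan has no session-group term and names no clustering sensitivity analysis, so its intervals are too narrow if outcomes within a group are positively correlated

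*Combined protocol and SAP*

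**What the plan says.** **Delivery.** Section 5 states: "The AAT intervention includes eight 60-minute group sessions". Section 5.2 says that active-arm "participants will receive an 8-week AAT program, and an 8-week BWL program, both using a group format". Section 5.1 agrees: the active arm "will first receive a weekly, group-based AAT program for the first two months", followed by two months of weekly NUTR group sessions. Section 8.4 adds: "Participants will attend 8 weekly AAT sessions and then transition to eight, weekly NUTR sessions".

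**Control arm.** Section 5.1 says that wait-list "participants will receive an abbreviated AAT treatment at the end of 6 months". The last assessment (T3) is also at the end of month 6. I read T3 as taken before that treatment starts, so from T1 to T3 only one arm is grouped by treatment.

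**Aim 2 model.** Sections 9.2 and 10.3 state: "Linear mixed effects modeling will be used to examine the association between treatment group assignment", coded as a 0/1 arm indicator, and the outcomes. They add: "Baseline scores will be used as covariates in these analyses with interactions between treatment group assignments with baseline values of outcome scores". They name no random effect at any level, and no session-group or facilitator term. Standardized residuals are to be examined, and Cohen's d is to be reported with a 95% interval.

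**Sensitivity analyses.** Section 10.1 says: "Sensitivity analyses will be performed to assess the robustness of the major results as indicated by their sensitivity to reasonable perturbations" of methods and assumptions. Clustering is not mentioned.

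**Sample size.** Section 10.6 gives power 0.80 at d = 0.74 with 60 women, evenly allocated. Elsewhere the target is 48 (24 per arm).

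**The concern.** Women in one session group share peers, a leader and a course of sessions, so their outcomes may be more alike than those of women in different groups. The documents do not show that this happens, but the design makes it plausible.

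A mixed model accounts only for the levels put into it. A woman-level random effect would handle the T2 and T3 repeats, but not correlation between different women in one group. If that correlation is positive, the variance of the active-arm mean is larger than the model assumes. Standard errors and Cohen's d intervals are then too small and p-values too low. Adjusting for baseline does not remove residual group correlation.

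These intervals are a planned output, and section 10.6 foresees a larger study if the pilot succeeds. Their width will therefore be read.

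**Working it through.** **1. The plan's own figure.** Inputs from 10.6: 30 per arm, d = 0.74, power 0.80. Alpha is not stated, so I assume two-sided 0.05. Noncentral-t power with noncentrality 0.74 × sqrt(30/2) is 0.805, and the normal approximation gives 0.818. One-sided 0.05 gives 0.88 to 0.89 and does not match. The stated 0.80 is thus reproduced for independent women without baseline adjustment. With 24 per arm the same calculation gives 0.71.

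**2. Effect of grouping one arm.** Let m be the group size. The design effect in the active arm is DE = 1 + (m − 1) × ICC, and in the control arm it is 1. With equal arms and about equal variances, the ratio of true to stated SE is sqrt((DE + 1)/2) = sqrt((2 + (m − 1) × ICC)/2). Type I error is 2 × (1 − Φ(1.96/ratio)). Group size and ICC are assumptions; the documents give neither.

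| m | ICC | DE | SE ratio | Type I error |
|---|---|---|---|---|
| 4 | 0.01 | 1.03 | 1.01 | 5.2% |
| 4 | 0.05 | 1.15 | 1.04 | 5.9% |
| 8 (24 per arm) | 0.05 | 1.35 | 1.08 | 7.1% |
| 10 | 0.01 | 1.09 | 1.02 | 5.5% |
| 10 | 0.05 | 1.45 | 1.11 | 7.7% |
| 10 | 0.10 | 1.90 | 1.20 | 10.4% |
| 15 | 0.10 | 2.40 | 1.30 | 13.3% |
| 30 (one group) | 0.05 | 2.45 | 1.31 | 13.6% |

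A simulation at one time point (100,000 replicates) agrees: with 3 groups of 10 and ICC 0.05, a nominal 95% interval covers about 92.4%. With one group of 30, the group effect could not be separated from treatment at all.

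**3. Which contrast the ratio applies to.** The planned arm-by-baseline interaction matters here. Unless baseline is centred, the arm coefficient is the effect at a baseline score of zero, and its SE is dominated by uncertainty in the slopes. I simulated one visit with 30 per arm, baseline mean 2 SD above zero and baseline-outcome correlation 0.5 (all assumed):

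- 3 groups of 10, ICC 0.05, factor 1.11. Centred contrast: true ratio about 1.11, coverage 92.3% before the factor and 94.9% after. Uncentred coefficient: true ratio about 1.02, coverage 94.4% before and 96.6% after.
- 2 groups of 15, ICC 0.10, factor 1.30. Uncentred coefficient: true ratio 1.07, coverage 98.2% after the factor.

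The sizes in step 2 therefore hold for the contrast at mean baseline, not for an uncentred arm coefficient.

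**4. Baseline adjustment.** The ICC that matters for the adjusted contrast is the residual one. Start from an unadjusted ICC of 0.05, groups of 10 and a baseline-outcome correlation of 0.3 to 0.6. Type I error after adjustment is then 7.9% to 9.1% if baseline explains none of the between-group variance, 6.5% to 7.1% if it explains half, and 5% if it explains all. The documents do not say which applies.

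**5. Net power.** At d = 0.74 and 30 per arm, adjustment with that correlation range raises power to 0.84 to 0.94 for independent women. With groups of 10, this becomes 0.76 to 0.89 at residual ICC 0.05 and 0.69 to 0.83 at 0.10. Net power may lie on either side of 0.80.

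**6. Can the trial estimate the ICC?** Not usefully. With a true ICC of 0.05, an ANOVA estimate is at or below zero in 44% of samples with 5 groups of 6, 47% with 3 of 10, and 54% with 2 of 15.

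**The case against.** The strongest reply has four parts.

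- **The plan leaves room for it.** A mixed model can hold a group effect, 10.1 promises sensitivity analyses under changed assumptions, and residuals are to be checked. This stands in part: a group term is not excluded. But none is stated, the clause in 10.1 permits a clustering analysis without planning one, and the residual check does not mention independence within groups.
- **The size is assumed.** This stands. The synopsis gives enrolment as January 2019 to July 2021, so small successive groups are possible. Groups of 4 at ICC 0.05 give a factor of only 1.04. The documents cannot place the trial within the range.
- **The stakes are low.** This also stands. Aim 2 is secondary, 10.6 calls the study exploratory and not a determination of efficacy, and 10.3 sets no decision rule for Aim 2. Type I error serves here as a scale for interval error, not as a decision risk.
- **A full remedy would be heavy.** Six outcomes, two visits, three ICC values, and both the contrast and Cohen's d would give 6 × 2 × 3 × 2 = 72 extra intervals. That is too much for a pilot of 48 to 60 women, so the fix is limited to binge eating.

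A reader might infer that the Aim 2 intervals are known to be wrong, or that grouping leaves the trial underpowered. The documents support neither. They contain no evidence of within-group correlation, and step 5 shows that the gain from baseline adjustment may outweigh the loss from grouping.

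**Conclusion.** The point holds as a conditional one. Treatment up to T3 is grouped in one arm only, the Aim 2 model states no term for it, and no clustering sensitivity analysis is named. If residual outcomes within a group are positively correlated, the intervals for the arm contrast at mean baseline and for Cohen's d are too narrow.

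Under assumed groups of 4 to 15, ICC 0.01 to 0.10 and equal arms, the factor is about 1.01 to 1.30. A single large group would be worse. Confidence in the direction is high, given positive correlation; confidence in the size is low. The matter is worth a short change before analysis but does not threaten the feasibility aim.

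**What to change.** **Data.** Record a session-group ID for each woman in each phase (AAT and NUTR/BWL). If membership is not recorded at the time, the analysis may be impossible later.

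**Section 10.3.**
- Centre the baseline score, or define each arm contrast at the overall mean baseline. Keep the planned model as the main analysis, with a stated woman-level random effect.
- Prespecify one clustering sensitivity analysis, at least for binge eating at T2 and T3. Report the centred contrast and its Cohen's d interval with the SE multiplied by sqrt((2 + (m − 1) × ICC)/2) at ICC 0.01, 0.05 and 0.10. Here m is the achieved group size, or Σm_j²/Σm_j if groups are unequal. For unequal arms use sqrt((DE/n1 + 1/n0)/(1/n1 + 1/n0)), with n1 the active arm and n0 the control arm.
- Use the residual ICC for the adjusted contrast and the unadjusted ICC for a Cohen's d from raw means. State which phase's groups define m if women are regrouped.
- For other outcomes, state that intervals assume independent women. Treat any estimated ICC as descriptive only.

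**Section 10.6.** State that 0.80 matches a calculation for independent women without baseline adjustment (two-sided 0.05 assumed) and makes no visible allowance for grouping.

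**Cost.** One ID variable per phase, some SAP wording, and 1 × 2 × 3 × 2 = 12 extra intervals for binge eating. With 3 groups of 10 and an assumed baseline-outcome correlation of 0.5, half-widths are 0.46, 0.50 and 0.54 SD at the three ICC values, against 0.45 SD under independence. An interval is too wide if the true ICC is below the fixed value: assuming 0.05 when 0.01 is true gives coverage 2Φ(1.96 × 1.107/1.022) − 1, about 96.6%. It is still too narrow if the true ICC is above: 92.8% when 0.10 is true. That is why a range is reported.
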